7.5.2.7. Serum Inflammatory Markers (Part B 20 mg and Part D only)

Serum samples will be analyzed for various inflammatory markers (Part B, 20 mg and Part D only), including interferon (IFN)- γ , interleukin (IL)-1 β , IL-2, IL-4, IL-6, IL-8, IL-10, IL-12p70, IL-13, and tumor necrosis factor (TNF)- α , using enzyme-linked immunosorbent assay (ELISA). The inflammatory marker testing is considered as exploratory and results will not be provided to or reviewed by the Investigator.

In addition to the time points specified in the schedule of assessments, ad hoc inflammatory marker testing may also be performed when immunogenicity is suspected, such as febrile and/or allergy/hypersensitivity events, or unexplained bronchospasm.

7.5.2.8. Pregnancy Test

A urine or serum beta-human chorionic gonadotropin (β -hCG) pregnancy test will be performed on all females, regardless of childbearing potential, at the initial screening visit, on Day -1 (Parts A and B) or Day 1 (Part D), and at discharge on Day 337 in Part A, Day 365 in Part B, or Day 341 in Part D of the study; or if pregnancy is suspected or upon withdrawal of a female subject from the study. The pregnancy test on Day -1 (Part A and Part B) or Day 1 (Part D) must be confirmed as negative before the subject can be enrolled and randomized.

7.5.2.9. Drug and Alcohol Screen

A blood or urine screen for drugs of abuse and alcohol will be performed at the initial screening visit. Additional drug and alcohol screens may be performed at the Investigator's discretion. Samples are to be tested for amphetamines, barbiturates, benzodiazepines, cocaine, methadone, opiate metabolite, and phencyclidine.

Results of drug and alcohol screens will be reviewed and verified by the study monitor, but will not be collected in the CRF. Any positive result for drugs of abuse or alcohol at the screening visit will exclude the subject from further participation in the study. Note that drug screen results that are positive for a drug of abuse may be acceptable with confirmation of valid prescription for medical use (eg, methylphenidate for the treatment of attention deficit hyperactivity disorder).

7.5.2.10. Viral Screen

At the initial screening visit, a blood sample of approximately 8.5 mL will be drawn into a serum separator tube to test for the presence of human immunodeficiency virus (HIV) type 1 or 2 antibodies, hepatitis B surface antigen (HBsAg), and hepatitis C virus (HCV) antibodies.

The test results must be confirmed negative at the screening visit. If a test result is positive, the subject will be excluded from enrolling into the study. Results of the viral screen will be reviewed and verified by the study monitor but will not be collected in the CRF database.

7.5.2.11. Electrocardiogram (ECG)

ECGs will be performed at the times specified in the Schedule of Procedures. The following parameters will be recorded: heart rate, PR, QRS, QT, QTcB, and QTcF. ECG interval measurements and interpretations will be centralized and performed by a single certified cardiologist.

The ECG collected on Day -1 will serve as the subject's baseline ECG for Parts A and B. The ECG collected during Screening will serve as the subject's baseline ECG for Part D. If there is a clinically significant change from baseline, the ECG change should be reported as an AE.

7.5.2.12. Spirometry

Spirometry will be performed according to the guidelines published by the American Thoracic Society for standardization of spirometry (American Thoracic Society 1995). The following parameters will be assessed during the spirometry testing:

- Forced expiratory volume in 1 second (FEV₁): absolute volume (L) and percent predicted for age, gender, and height.
- Forced vital capacity (FVC): absolute volume (L) and percent predicted for age, gender, and height.
- FEV₁/FVC: ratio and percent predicted for age, gender, and height.
- Forced expiratory flow over the middle one-half of the FVC (FEF_{25-75%}): absolute volume (L) and percent predicted for age, gender, and height.

The parameters will be normalized using the ERS Global Lung Function Initiative (GLI) prediction equations.³³ The average of the results from the testing on Day -1 and at pre-dose on Day 1 will serve as the subject's baseline for Parts A and B. The average of the results from the testing on Screening and at pre-dose on Day 1 will serve as the subject's baseline for Part D.

Instructions on Bronchodilator Use in Relation to Spirometry Testing

- If feasible for the subject, all spirometry testing should be performed "pre-bronchodilator" if the subject is receiving treatment with a short-acting beta-agonist or anticholinergic bronchodilator (eg, beta-agonist medication such as albuterol or anticholinergic agent such as ipratropium bromide). These medications should be withheld for at least 4 hours before spirometry testing.
- If the subject is receiving treatment with a long-acting bronchodilator (eg, salmeterol), these medications do not have to be withheld and spirometry testing can be performed at any time in relation to dosing with the long-acting bronchodilator.

Instructions on Subject's Routine Pulmonary Therapies in Relation to Spirometry Testing

- For testing consistency within a subject, it is suggested that all spirometry testing for a subject be consistently performed either before or after receiving their daily routine pulmonary therapies (airway clearance and pulmonary medications). It will be at the discretion of the Investigator and study staff to determine what is most feasible for each subject and to maintain this testing consistency throughout the study.

If a subject is experiencing respiratory distress or respiratory symptoms, based on the judgment of the Investigator, unscheduled spirometry testing may be performed when the subject is stable.

7.5.2.13. Chest x-ray

Chest x-rays will consist of routine posterioranterior and lateral views.

- For all subjects participating in the study, the baseline chest x-ray may be performed at any time from Day -14 to Day -2 (Parts A and B) or any time from Day -14 to Day -1 (Part D) during the screening period.
- In Part A, chest x-rays are scheduled on Day 8 and Day 29 of the study, representing intervals of 1 and 4 weeks after administration of the single dose of IP.
- In Part B, chest x-rays are scheduled on Day 36 and Day 57 of the study, representing intervals of 1 and 4 weeks after administration of the fifth dose of IP.
- In Part D, chest x-rays are scheduled on Day 11 and Day 32 of the study, representing intervals of 1 and 4 weeks after administration of the 5th dose of IP.

At the Investigator's discretion, a chest x-ray may be performed at any time during the study if the subject is experiencing respiratory symptoms that warrant it.

7.5.2.14. Measurement of [REDACTED] mRNA and [REDACTED] in Blood

See the Laboratory Manual for instructions on collection and handling of samples.

Whole blood samples will be analyzed for [REDACTED] mRNA and [REDACTED] levels. In Part A, a baseline sample will be obtained on Day -1 and post-treatment samples will be collected on Day 1 (at 8 hours), and on Days 2, 8, 15, and 29. In Part B, a baseline sample will be obtained on Day -1 and post-treatment samples will be collected on Days 2, 8 (pre-dose), 29 (pre-dose), 30, 36, 43, and 57. In Part D, a baseline sample will be obtained pre-dose on Day 1 and post-treatment samples will be collected on Day 1 (2 hours post-dose), Days 2 (pre-dose and 2 hours post-dose), 3 (pre-dose and 2 hours post-dose), 4 (pre-dose and 2 hours post-dose), 5 (pre-dose and 2 hours post-dose), 11, 18 and 32.

The quantification of [REDACTED] mRNA will be performed by qPCR on RNA purified from the whole blood sample. qPCR results will be reported as the number of copies of [REDACTED] mRNA per μ g of total RNA.

The quantification of [REDACTED] in whole blood samples will be performed by high performance liquid chromatography/mass spectrometry.

In addition to the time points specified in the schedule of assessments, ad hoc testing for measuring [REDACTED] mRNA and [REDACTED] may also be performed when immunogenicity is suspected, such as febrile and/or allergy/hypersensitivity events, or unexplained bronchospasm.

7.5.2.15. Measurement of Immune Responses to CFTR Protein

See the Laboratory Manual for instructions on collection and handling of samples.

The presence of potential antibodies to CFTR protein will be measured by an enzyme-linked immunosorbent assay in serum samples collected on Days -1 (baseline), 15, 29, 85, 169, and 337

(optional) in Part A; and on Days -1 (baseline), 36, 57, 113, 197, and 365 (optional) in Parts B; and on Days 1 (pre-dose, baseline), 11, 18, 32, 145, 229, 341 (optional) in Part D. Antibodies to PEG will also be measured.

CFTR-specific T cell responses will be assessed using peripheral blood mononuclear cells collected at the same time points. T cell responses to CFTR will be measured by a human interferon- γ enzyme-linked immunospot assay as described by Calcedo et al.³⁴

As noted above, the blood collections for these assays on the final study day (Day 337 in Part A; Day 365 in Part B; Day 341 in Part D) are optional. The blood collection for any of these assays will only be taken if there has been a de novo positive result detected at one or more post-treatment time points. In the event of inconclusive, invalid, or missing assay results at the Day 169, Day 197, or Day 145 visit for Part A, Part B, or Part D, respectively, the blood collection for one or more of these assays will be taken at the final study day at the discretion of the Sponsor.

In addition to the time points specified in the schedule of assessments, ad hoc immunogenicity testing may also be performed when immunogenicity is suspected, such as febrile and/or allergy/hypersensitivity events or unexplained bronchospasm.

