d Assays will measure antibody and T cell responses to CFTR protein and anti-PEG antibodies. The blood collections for any of these assays on the final study day (Day 341) are optional and will be driven by the observation of a de novo positive immune response after treatment (see Section 7.5.2.15). In the event of inconclusive, invalid, or missing assay results at the Day 145 visit, the blood collection for one or more of these assays will be taken at Day 341 at the discretion of the Sponsor.

e In addition to the time points specified in the schedule of assessments, ad hoc testing for immune response assays, inflammatory markers, and/or mRNA and [REDACTED] may also be performed when immunogenicity is suspected, such as febrile and/or allergy/hypersensitivity events or unexplained bronchospasm.

f A serum or urine β-hCG pregnancy test will be performed on all female subjects, regardless of childbearing potential, at the end of the study on Day 341. In addition, a serum or urine β-hCG pregnancy test should be performed on female subjects at any time pregnancy is suspected or upon withdrawal from the study (the latter applies to all female subjects, regardless of childbearing potential).

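### Part D's fallback immune-response sample on Day 341 is triggered only by a failed Day 145 result, so a failed or missed Day 229 sample has no stated route to a replacement

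*Protocol*

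**What the plan says.** Protocol Section 7.5.2.15 sets the days for the CFTR antibody, anti-PEG antibody and CFTR T cell samples:

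- Part A: "serum samples collected on Days -1 (baseline), 15, 29, 85, 169, and 337", the last of these optional.
- Part B: "on Days -1 (baseline), 36, 57, 113, 197, and 365 (optional) in Parts B".
- Part D: "on Days 1 (pre-dose, baseline), 11, 18, 32, 145, 229, 341 (optional) in Part D".

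The same section gives two routes to the optional final-day sample. The first is a positive finding: the sample "will only be taken if there has been a de novo positive result detected at one or more post-treatment time points". The second is the fallback, which applies "In the event of inconclusive, invalid, or missing assay results at the Day 169, Day 197, or Day 145 visit". These three visits belong to Parts A, B and D in that order; when the fallback applies, the Sponsor may decide to have one or more of the assays drawn on the final day. Table 9 footnote d repeats the Part D fallback with the same visit: "In the event of inconclusive, invalid, or missing assay results at the Day 145 visit". Neither place names Day 229 as a trigger, although Table 9 marks an immune-response sample on that day.

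Separately, Section 7.5.2.15 allows ad hoc testing when immunogenicity is suspected.

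**The concern.** A fallback sample is most useful when it protects the last planned observation. In Part D it does not. A failed Day 145 sample is followed by the Day 229 sample anyway. A failed or missed Day 229 sample is followed only by the optional Day 341 sample, and for a subject who has stayed negative the rule does not open that route.

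Losing Day 229 is plausible. Protocol Section 7.6 lets in-person visits be replaced by telephone visits because of COVID-19. It ranks Days 11, 32 and 341 as the highest-priority Part D visits outside dosing days, and Day 229 is not among them. The home-visit assessments it gives as examples do not mention immune assays. The visit most likely to be kept in person, Day 341, is thus the one where a lost Day 229 sample could be replaced.

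At stake is late antibody and T cell information. Section 3.1 treats it as part of the safety evaluation, and Section 1.5 gives the possibility of persistent immunogenicity as a reason for not studying healthy volunteers. Part D is the only daily-dosing cohort, with 6 active and 2 placebo subjects (SAP Section 2.5).

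**Working it through.** **Inputs.** Sampling days and trigger visits come from Protocol Section 7.5.2.15, with Table 9 and its footnote d for Part D. Last dosing days are Day 1 (Part A), Day 29 (Part B) and Day 5 (Part D), from Sections 7.1.2, 7.2.2 and 7.3.2. Blood volumes come from Appendix 4.

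**Step 1: reproduce the plan's own count.** The Part D days are 1, 11, 18, 32, 145, 229 and 341, which is 7 samples. Appendix 4 also gives 7 for each assay, including the optional Day 341 sample: 7 × 4.0 = 28.0 mL (antibody) and 7 × 20.0 = 140.0 mL (T cell). The Part D total is 8.5 + 93.5 + 44.0 + 49.5 + 8.0 + 65.0 + 32.5 + 28.0 + 140.0 = 469.0 mL, as stated. Day 229 is therefore a planned sample, and the Day 341 draw is already budgeted.

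**Step 2: compare the trigger visit with the last non-optional sample.** Days after last dose = study day − last dosing day.

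| Part | Last non-optional sample | Days after last dose | Trigger visit | Days after last dose | Same visit? |
|---|---|---|---|---|---|
| A | Day 169 | 169 − 1 = 168 | Day 169 | 168 | Yes |
| B | Day 197 | 197 − 29 = 168 | Day 197 | 168 | Yes |
| D | Day 229 | 229 − 5 = 224 | Day 145 | 145 − 5 = 140 | No |

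**Step 3: follow the Part D rule for a subject with no de novo positive result.**

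- Day 145 fails, Day 229 valid: last valid result at 224 days. The Sponsor may also request Day 341.
- Day 145 valid, Day 229 fails or is missed: neither route to Day 341 is met. The last valid result is at 140 days.
- Both fail: the Day 145 trigger applies and the Sponsor may request Day 341.

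Only the second case is left without a stated route.

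**Step 4: put the gap in context.** Follow-up after the last dose is 336 days in every part (337 − 1, 365 − 29, 341 − 5). In the second case, 341 − 145 = 196 days follow the last valid sample, or 196/336 = 58%. Parts A and B, run exactly as planned with no positive result, leave 337 − 169 = 168 and 365 − 197 = 168 days, or 168/336 = 50%. Against that routine standard, the affected Part D subject is 168 − 140 = 28 days short. Against Part D's own plan the shortfall is 224 − 140 = 84 days.

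**The case against.** The strongest reply is that Day 145 may be deliberate. The protocol never says that the fallback follows the last non-optional sample; that pattern is inferred from Parts A and B. Another pattern fits all three parts: each ends with three late clinic visits (Days 169, 253 and 337; 197, 281 and 365; 145, 229 and 341), and the trigger is always the first. Day 145 is also the Part D sample closest to the 168-day timing of the other parts (28 days away, against 224 − 168 = 56 for Day 229). Section 7.5.2.15 and Table 9 footnote d agree with each other. This stands: a reader might infer a proven error or an internal contradiction, and the documents do not support that. It does not explain why Day 229 is left uncovered.

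A reader might also infer that the rule forces an unneeded 24 mL draw (4.0 + 20.0) on Day 341 when Day 145 fails and Day 229 is valid. It does not. The Sponsor can decline, and the draw is already in the 469.0 mL.

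Other routes narrow the gap. A de novo positive at any other post-treatment visit opens Day 341. Ad hoc testing is allowed on suspicion, and Section 7.5.2 allows unscheduled tests needed for safety. Section 7.3 makes visit windows advisory, so a missed Day 229 sample might be drawn late. None of these is prompted by an invalid assay in a negative subject without symptoms.

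Finally, the immune assays are not named in the primary or secondary endpoint, in SAP Section 9.1's list of safety measures, or in the SAP's planned tables and listings. That also stands and limits the consequence.

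**Conclusion.** The gap is real but small. For a Part D subject with no de novo positive result and no suspected immunogenicity, a valid Day 145 result followed by a failed or missed Day 229 assay leaves no stated route to a Day 341 sample. The last valid result is then 140 days after the last dose instead of 224.

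The 58% figure should not be read as the size of the harm. It applies only to a subject who loses that one sample, and the comparable figure is 50% in Parts A and B when nothing goes wrong. Nor does the fallback guarantee a sample where it applies, because it is discretionary. A Day 341 sample would be 341 − 229 = 112 days later than the one it replaces, so it would restore late coverage but not the Day 229 time point.

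The conclusion assumes that the rule is applied as written and that the other routes are not used. The documents give no rate of failed or missed samples, so the expected number of affected subjects cannot be stated; the ceiling is the 8 planned for Part D. No sample size, endpoint or planned SAP display changes. This is a worthwhile clarification of the sampling rule.

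**What to change.** In Section 7.5.2.15 and in Table 9 footnote d, make the Part D trigger a failed or missing result at Day 145 or Day 229. If the Sponsor confirms that Day 145 was merely carried over, name Day 229 alone. Keep the Sponsor's discretion, so that no draw is taken when a valid later result already exists.

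The change adds no visit, since Day 341 is already a clinic visit, and no blood beyond the 469.0 mL in Appendix 4. The cost is a minor wording amendment in two places, with the Sponsor and IRB approval that Section 10.3.2 requires for protocol amendments.

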7.5.3. Volume of Blood to be Drawn from Each Subject

The assessments, the number of samples and sample volumes for each assessment, and total volume of blood to be drawn from each subject are presented in [Appendix 4](#).

During Part A of the study, approximately 350.5 mL of blood will be drawn from all subjects, regardless of sex, over the duration of the study (up to 368 days or approximately 53 weeks). During Part B of the study, approximately 405.5 mL of blood will be drawn from all subjects, regardless of sex, over the duration of the study (up to 396 days or approximately 57 weeks). During Part D of the study, approximately 469.0 mL of blood will be drawn from all subjects, regardless of sex, over the duration of the study (up to 372 days or approximately 54 weeks). These volumes include the optional blood samples to be collected on the final study day (Day 337 in Part A; Day 365 in Part B; Day 341 in Part D), if needed for assessment of immune responses to CFTR protein (Section [7.5.2.15](#)).

When more than one blood assessment is to be done at the time point, the assessments may be combined if they require the same type of tube.

The total amount of blood to be drawn is an estimate, as it may vary depending on the study center's sample volume requirements for the safety tests (serum chemistry, hematology, coagulation, CRP), pregnancy test (β -hCG), and viral screen (HIV, HBsAg, and HCV tests).

7.5.4. Cystic Fibrosis Questionnaire-Revised (CFQ-R)

The Cystic Fibrosis Questionnaire-Revised (CFQ-R; version for adolescents and adults [patients 14 years old and older]) will be completed by Part B subjects at baseline on Day -1, and on Days 36, 43, 57, 85, 113, 197, 281, and 365.³⁵ The results of the respiratory domain of the CFQ-R will

be of primary interest; the minimal change from baseline representing a clinically important improvement in the respiratory domain was determined to be ≥ 4 .³⁶

7.6. Coronavirus Disease Contingency Measures

Consistent with FDA Guidance on the conduct of clinical trials during the coronavirus disease (COVID-19) public health emergency (March 2020), ensuring the safety of trial participants is paramount. Public health measures implemented by Federal and State authorities to control the COVID-19 pandemic have made compliance with protocol-mandated in-person study visits unfeasible. As such, protocol-mandated in-person study visits may be conducted as telephone visits to query the subject about the occurrence of any AEs/SAEs and any changes in concomitant medications or surgical procedures. Such changes from the protocol will be captured as protocol deviations due to COVID-19.

For subjects participating in Part A, the clinic visits at Day 29 and Day 337 are the highest priority and should be conducted in-person within 4 weeks of the target visit date, if possible.

For subjects participating in Part B, other than the clinic visits on dosing days (which are mandatory), clinic visits during the treatment period (through Day 30), as well as at Days 36, 57, and 365 are the highest priority and should be conducted in-person within 4 weeks of the target visit date, if possible.

For subjects participating in Part D, other than the clinic visits on dosing days (which are mandatory), the clinic visits at Day 11, Day 32, and Day 341 are the highest priority and should be conducted in-person within 4 weeks of the target visit date, if possible.

At the discretion of the Sponsor and with subject consent, planned onsite visits (excluding dosing visits) may be conducted at the subject's home (or designated space) by a study coordinator or qualified home health professional, as available. Assessments conducted at these visits will be focused on patient safety and may include collection of safety labs, vital signs, ECG, adverse events, concomitant medications/surgical procedures.

As the epidemiological conditions and risks may differ across different geographies in the United States, the threat of COVID-19 may differ at each clinical site. Once the risk has diminished in a particular region as determined by Federal and State public health officials and subjects and site staff are comfortable returning to in-person visits, all protocol-mandated in-person study visits should resume as planned.

8. ADVERSE AND SERIOUS ADVERSE EVENT ASSESSMENT

8.1. Definition of Adverse Events, Period of Observation, Recording of Adverse Events

An **AE** is any untoward medical occurrence in a clinical investigation subject administered a pharmaceutical product and that does not necessarily have a causal relationship with this treatment. An AE can therefore be any unfavorable and unintended sign (including an abnormal laboratory finding), symptom, or disease temporally associated with the use of a medicinal (investigational) product, whether or not related to the medicinal (investigational) product (ICH Guidance E2A 1995).

Where possible, a diagnosis rather than a list of symptoms should be recorded. If a diagnosis has not been made, then each symptom should be listed individually. If a pulmonary exacerbation is suspected, sufficient information should be recorded to determine if the event can be classified as a pulmonary exacerbation based on the criteria defined in Section 8.1.7. All AEs should be captured on the appropriate AE pages in the CRF and in source documents. In addition to untoward AEs, unexpected benefits outside the IP indication should also be captured on the AE CRF.

All AEs and SAEs, regardless of relationship, will be collected for each subject from the time the subject signs the informed consent until study completion, which is defined as the last study assessment for that subject on Day 337 (± 3 days) in Part A, Day 365 (± 3 days) in Part B, or Day 341 (± 3 days) in Part D of the study. As such, all AEs and SAEs will be collected throughout the study for each subject.

All AEs must be followed to closure (the subject's health has returned to his/her baseline status or all variables have returned to normal), regardless of whether the subject is still participating in the study. Closure indicates that an outcome is reached, stabilization achieved (the Investigator does not expect any further improvement or worsening of the event), or the event is otherwise explained. When appropriate, medical tests and examinations are performed so that resolution of event(s) can be documented.

If the Investigator considers it necessary to report an AE in a study subject after the end of the study, he or she should contact the Medical Monitor to determine how the AE should be documented and reported.

